**Any Grade 3 ADRs require treatment discontinuation, except for any of the following:**

- Transient Grade 3 flu-like symptoms or fever that is controlled with medical management
- Transient Grade 3 fatigue, local reactions, headache, nausea, emesis that resolves to  $\leq$  Grade 1
- Tumor flare phenomenon defined as local pain, irritation, or rash localized at sites of known or suspected tumors
- Any Grade  $\geq$  3 drug-related amylase or lipase abnormality that is not associated with symptoms or clinical manifestations of pancreatitis
- Grade 3 Hgb decrease ( $< 8.0$  g/dL) that is clinically manageable with blood transfusions or erythroid growth factor use
- Keratoacanthoma (KA) and cutaneous squamous cell carcinoma (cSCC).

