### 6.6.1 Adverse Drug Reactions Requiring Treatment Modification

Any adverse drug reaction (ADR) assessed as related to M7824 may require permanent or transient discontinuation of M7824 treatment. For the management of certain ADRs assessed to be irAEs, follow the American Society of Clinical Oncology (ASCO) guideline in [Appendix 6](#). Single laboratory values out of the normal range that do not have any clinical correlate do not necessarily need treatment interruption. Questions or concerns with regard to management and/or follow-up of ADRs should be discussed with the Medical Monitor.

Immune-related AEs, IRRs including hypersensitivity, anemia, TGF- $\beta$  inhibition mediated skin reactions, and bleeding events are managed and followed up as described in their respective sections. Permanent study intervention discontinuation may be recommended, so the relevant section must be reviewed:

- For suspected irAEs, irAE management and guidance is presented in [Appendix 6](#). General management by NCI-CTCAE v5.0 toxicity grading, as per ASCO, is listed below:
  - Grade 1: study intervention should be continued with close monitoring, with the exception of some neurologic, hematologic, and cardiac toxicities.
  - Grade 2: study intervention may be suspended for most Grade 2 toxicities, with consideration of resuming when symptoms revert to Grade 1 or less. Corticosteroids may be administered (initial dose of 0.5 to 1 mg/kg/day of prednisone or equivalent).
  - Grade 3: study intervention is generally suspended and the high-dose corticosteroid treatment (prednisone 1 to 2 mg/kg/day or methylprednisolone 1 to 2 mg/kg/day) should be initiated. Corticosteroids should be tapered over the course of at least 4 to 6 weeks. Some refractory cases may require infliximab or other immunosuppressive therapy.

- Grade 4: in general, permanent discontinuation of study intervention is recommended, with the exception of endocrinopathies that have been controlled by hormone replacement.
- IRRs and hypersensitivity reactions guidance are presented in Section 6.9.1.
- Guidance on anemia is presented in Section 6.9.4.
- Guidance and management for TGF- $\beta$  inhibition mediated skin reactions are discussed in Section 6.9.3.
- Guidance and management of bleeding events are discussed in Section 6.9.5.

In general, the following applies for ADRs related to M7824 that are not covered by the ASCO guideline:

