**Any Grade 4 ADRs require permanent treatment discontinuation, except endocrinopathies that have been controlled by hormone replacement, or single laboratory values out of normal range that do not have clinical relevance.**

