- Grade 3: study intervention is generally suspended and high-dose corticosteroids (prednisone 1 to 2 mg/kg/day or methylprednisolone 1 to 2 mg/kg/day) treatment should be initiated. Corticosteroids should be tapered over the course of at least 4 to 6 weeks. Some refractory cases may require infliximab or other immunosuppressive therapy.
- Grade 4: in general, permanent discontinuation of study intervention is recommended, with the exception of endocrinopathies that have been controlled by hormone replacement.

Permanent treatment discontinuation is required in case of immune-related Grade 4 rash/inflammatory dermatitis, nephritis, autoimmune hemolytic anemia, hemolytic uremic syndrome, aplastic anemia, immune thrombocytopenia and acquired thrombotic thrombocytopenic purpura (TTP).

For Grade 4 immune-related lymphopenia, permanent discontinuation of study intervention will be required, if lymphopenia is considered immune-related in nature, no clear alternative explanation exists for the event, and Grade 4 lymphopenia does not resolve within 14 days. Permanent discontinuation of study intervention is not required when the AE is manifest by a single laboratory value out of normal range without any clinical correlates. In this case, study intervention should be held until the etiology is determined. If the event is not considered immune-related and resolves to Grade  $\leq 1$  restarting of study intervention may be considered.

For additional organ/system specific management guidelines, see the guideline tables in [Appendix 6](#).

Recommended guidance and management for specific irAEs are provided in the current NCCN guideline available at <http://www.nccn.org>.

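### Protocol Section 6.6.1 covers an asymptomatic Grade 4 amylase or lipase rise in both its Grade 4 stopping rule and an exception in its Grade 3 list, and the two can be read to give opposite instructions.

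*Protocol*

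**What the plan says.** Protocol Section 6.6.1 gives stopping rules by grade for adverse drug reactions (ADRs). It introduces them with "In general, the following applies for ADRs related to M7824 that are not covered by the ASCO guideline".

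- **Grade 4.** "Any Grade 4 ADRs require permanent treatment discontinuation". There are two exceptions. One is for endocrine disorders under control on hormone replacement. The other is for "single laboratory values out of normal range that do not have clinical relevance". Amylase and lipase are not named.
- **Grade 3.** "Any Grade 3 ADRs require treatment discontinuation, except for any of the following". One listed item is written for Grade 3 or higher and covers any "drug-related amylase or lipase abnormality that is not associated with symptoms or clinical manifestations of pancreatitis". It sets no condition on whether the value is single or repeated.

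Earlier, the same section says: "Single laboratory values out of the normal range that do not have any clinical correlate do not necessarily need treatment interruption". The protocol defines neither *single* nor clinical relevance.

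**The concern.** Grade 3 or higher includes Grade 4, so an item in the Grade 3 list reaches into territory that the Grade 4 rule already governs on different conditions. Two sites with the same results could act in opposite ways: one stops M7824 for good, the other continues.

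The situation is foreseeable. Amylase and lipase are in the biochemistry panel (Protocol Appendix 5, Table A), and full serum chemistry is drawn every 2 weeks during treatment (Table 1), so a persistent rise would be seen repeatedly. Section 6.9.2 lists pancreatitis among the important potential risks. Section 7.1 refers withdrawal for ADRs back to Section 6.6.1. The decision then feeds the SAP summaries of exposure (Section 13) and of adverse events leading to permanent discontinuation (Section 15.1.2).

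**Working it through.** No arithmetic applies. The check sets the texts side by side.

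**Step 1: which rules govern.** The rules by grade apply where the ASCO-based guidance in Appendix 6 does not. The gastrointestinal table there (Table A2) covers colitis and hepatitis. No Appendix 6 table gives management for raised amylase, raised lipase or pancreatitis. The general rules of Section 6.6.1 therefore apply.

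**Step 2: the conditions of each exception.** The Grade 4 laboratory exception has two: the value is single, and it has no clinical relevance. The amylase/lipase exception also has two: the grade is 3 or higher, and there is no clinical picture of pancreatitis.

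**Step 3: apply both to a drug-related enzyme ADR without signs of pancreatitis.**

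| Case | Grade 4 rule | Amylase/lipase exception | Result |
|---|---|---|---|
| Grade 3, single or repeated | does not apply | exempt | no conflict |
| Grade 4, single, not clinically relevant | exempt | exempt | no conflict |
| Grade 4, repeated, not clinically relevant | stop, if *single* means one measurement; exempt, if it means an isolated laboratory finding | exempt | conflict on the first reading only |
| Grade 4, judged clinically relevant | stop | exempt | conflict on either reading |

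**Step 4: can the documents settle what *single* means?** The nearest text is the Grade 4 lymphopenia paragraph in Section 6.9.2. It requires permanent discontinuation when, among other conditions, the finding has not resolved within 14 days, and then says this is not required "when the AE is manifest by a single laboratory value out of normal range without any clinical correlates". The contrast with 14 days of non-resolution suggests that *single* means not persistent. The reference to clinical correlates, which also appears in Section 6.6.1, suggests an isolated laboratory finding. Neither reading is proved.

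**Step 5: is there an order of precedence?** None is stated.

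**Step 6: what follows from a stop.** The note to the tumor evaluation row of Table 1 says that, if treatment ends for a reason other than progression, tumor assessments continue on the original schedule until confirmed progression. The ITT set contains everyone who received at least one dose (Protocol Table 9; SAP Section 8.2). A stop under this rule therefore changes exposure and discontinuation counts. It does not change the response-rate denominator or the scan schedule.

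**The case against.** The strongest reply is that the named exception qualifies the general rule. The amylase/lipase item is the only text in Section 6.6.1 that mentions these enzymes, and the whole block is introduced as applying in general. The section also says that recommendations by grade differ with the specific toxicity, and it sends questions about managing ADRs to the Medical Monitor. A sensible site might well follow the specific item. This softens the conflict without resolving it. The Grade 4 rule is worded as a requirement and gives the Medical Monitor no stated role, whereas the Grade 2 rule does so expressly.

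A second reply is that an item under a Grade 3 heading can lift only the Grade 3 rule. In that case the words extending it above Grade 3 do nothing. The other items in that list that state a grade say Grade 3 alone, so a site could reasonably take this one as meant to reach Grade 4.

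Three stronger readings are tempting, and the documents do not support them:

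- A reader might infer that the Grade 4 rule plainly demands a permanent stop for every repeated asymptomatic rise. That depends on *single* meaning one measurement, which is not stated.
- A reader might infer that every participant with such values is caught. Appendix 4 says abnormal laboratory findings are not reported as adverse events unless they come with clinical signs and symptoms, lead to discontinuation, or are considered medically important. An asymptomatic rise is therefore not automatically an ADR.
- A reader might infer that the primary response analysis or response follow-up is at risk. Step 6 of the working shows otherwise.

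**Conclusion.** The overlap at Grade 4 is real, and the two texts can be read to give opposite instructions. The conflict is firm for a Grade 4 enzyme ADR without signs of pancreatitis that is judged clinically relevant. For a repeated value it is conditional on *single* meaning one measurement.

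The consequence is limited to inconsistent site decisions on permanent discontinuation, and through them to exposure and adverse-event discontinuation counts. The number affected cannot be derived: the documents give no frequency for such rises and do not reproduce the NCI-CTCAE grade criteria for the two enzymes. It is probably small. The point is worth correcting because the decision is permanent for the participant and the correction is cheap. It does not put the primary analysis in doubt.

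**What to change.** Reconcile the Grade 4 rule with the amylase/lipase item in the Grade 3 list so that Grade 4 abnormalities of these enzymes fall under one rule. Define what Section 6.6.1 means by single laboratory values: one measurement, or an isolated laboratory finding whether or not it is repeated. The sponsor's medical team must decide which rule applies; this review takes no position on that.

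The cost is a line or so of protocol wording plus the definition, with the ethics approval that Appendix 2 requires for an amendment. No planned analysis changes. The practical reach is limited: SAP Section 9 says the last participant started treatment on 3 January 2020, so the clarification would help only those still on treatment or reinitiating it.

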**Any Grade 2 ADRs should be managed as follows:**

If a Grade 2 ADR resolves to Grade  $\leq$  1 by the day before the next infusion, study intervention may be continued.

If a Grade 2 ADR does not resolve to Grade  $\leq$  1 by the day before the next infusion, but it is manageable and/or not clinically relevant, the Medical Monitor should be consulted to assess if it is clinically reasonable to administer the following infusion.

Note that treatment recommendations regarding continuation, hold, or discontinuation by grade are different depending on the specific toxicity (see [Appendix 6](#)). Toxicity grading is assigned based on NCI-CTCAE v5.0. The ASCO guideline should be used only for the management of immune-related toxicity due to M7824.

## 6.7

### Study Intervention After the End of the Study

After a participant has completed the study, has withdrawn consent, or has been withdrawn early, symptom guided appropriate treatment will be administered, if required, in accordance with the study site's standard of care and generally accepted medical practice and depending on the participant's individual medical needs.

On withdrawal from the study, participants may receive whatever care they and their physicians agree upon.

## 6.8

### Special Precautions

As a part of safety-related precautionary measures, a standardized risk management approach is planned for M7824 for IRRs, irAEs, TGF- $\beta$  inhibition mediated skin reactions, anemia, and bleeding AEs. The approach is mainly based on the mechanism of PD-L1 inhibition and TGF- $\beta$  inhibition.

## 6.9

### Management of Adverse Events of Special Interest and other Potential Risks

Adverse events of special interest (AESIs) are serious or non-serious AEs specific to the known mechanism of action of the study intervention that are of clinical interest requiring ongoing monitoring.

For this study, AESIs include the following:

- Infusion-related reactions including hypersensitivity
- Immune-related AEs
- TGF- $\beta$  inhibition mediated skin reactions
- Anemia
- Bleeding AEs

#### 6.9.1

### Infusion-Related Reactions Including Hypersensitivity

Infusion-related reactions, including hypersensitivity, are defined in this section. Infusion-related reactions are AESIs and identified risks for M7824.

#### Infusion-Related Reactions

Infusion-related reactions are defined as any signs or symptoms experienced by participants during the infusion of pharmacologic or biologic agents or any event occurring during or within 1 day of study intervention administration. They are identified based on a list of Medical Dictionary for Regulatory Activities (MedDRA) preferred terms and criteria on the timely relationship to an infusion. Events are divided into reactions versus signs and symptoms:

- Reactions are considered when onset is on the day of infusion (during or after the infusion) or the day after the infusion (irrespective of resolution date) for IRR, drug hypersensitivity, anaphylactic reaction, hypersensitivity, and type 1 hypersensitivity.
- Signs and symptoms of IRRs and hypersensitivity/allergic reactions are considered when onset is on the day of infusion (during or after the infusion) and resolved completely with the end date within 2 days after onset of (but not limited to) pyrexia, chills, flushing, hypotension, dyspnea, wheezing, back pain, abdominal pain, and urticaria.

### Management of Infusion-Related Reactions

Based on the observed low IRR incidence in Phase I studies in over 670 participants treated with M7824 single agent, and with low-grade IRRs without leading to treatment discontinuation, the first 15 participants will not receive premedication before first and second M7824 infusions in this study in order to establish whether mandatory use of premedication is required. If IRR is observed at the first or second infusion, premedication should be used for subsequent infusions at the discretion of the Investigator.

If two or more Grade 2 IRRs are seen during the first 2 infusions for the first 15 participants, an Independent Data Monitoring Committee (IDMC) will determine if mandatory premedication is needed. Study enrollment will continue in parallel to this review and sites will be notified accordingly if premedication will be required.

If IDMC determines mandatory premedication is justified in order to mitigate potential IRRs, premedication with an antihistamine and with paracetamol (acetaminophen) (e.g., 25 to 50 mg diphenhydramine and 500 to 650 mg paracetamol [acetaminophen] intravenous or oral equivalent) prior to each dose of M7824 is mandatory for the first 2 infusions. After the first 2 infusions, premedication is optional and at the discretion of the Investigator. If Grade 2 IRRs are seen during the first 2 infusions, then premedication should not be stopped. Steroids as premedication are not permitted.

Management of symptoms should follow the guidelines shown in [Table 4](#).

Table 4

## Treatment Modification of M7824 for Symptoms of Infusion-Related Reactions Including Immediate Hypersensitivity

NCI-CTCAE v5.0 Grade	Treatment Modification
Grade 1 – mild 

Mild transient reaction; infusion interruption not indicated; intervention not indicated.

	

Increase monitoring of vital signs as medically indicated as participants are deemed medically stable by the attending Investigator.

Grade 2 – moderate 

Therapy or infusion interruption indicated but if responds promptly to symptomatic treatment (e.g., antihistamines, NSAIDs, narcotics, IV fluids); prophylactic medications indicated for <math>\leq</math> 24 hours.

	

Stop the infusion of the study intervention caused IRR.

Increase monitoring of vital signs as medically indicated as participants are deemed medically stable by the attending Investigator.

If symptoms resolve quickly or decreased to Grade 1, resume infusion at 50% of original rate with close monitoring of any worsening otherwise dosing held until resolution of symptoms with mandated premedication for the next scheduled visit.

If worsens to Grade 3 or 4, follow treatment modification guidelines accordingly.

Grade 3 or Grade 4 – severe or life-threatening 

Grade 3: Prolonged (e.g., not rapidly responsive to symptomatic medication and/or brief interruption of infusion); recurrence of symptoms following initial improvement; hospitalization indicated for clinical sequelae.

Grade 4: Life-threatening consequences; urgent intervention indicated.

	

Stop the infusion of study intervention-caused IRR immediately and disconnect infusion tubing from the participant with additional appropriate medical measures and closely monitor until deemed medically stable by the attending Investigator. Hospitalization and/or close monitoring is recommended

Administration of glucocorticoids may be required

Restart the medication taking out the drug that is the cause of IRRs from the next scheduled visit

IRR=infusion-related reaction, IV=intravenous, NCI-CTCAE=National Cancer Institute-Common Terminology Criteria for Adverse Event, NSAIDs=nonsteroidal anti-inflammatory drugs.

Once the M7824 infusion is interrupted or rate reduced to 50% of previous infusion rate, it must remain decreased for all subsequent infusions. For Grade 3 or 4 IRRs, M7824 discontinuation is mandated.

For all types and grades of infusion reactions, details about drug physical constitution, method of preparation, and infusion must be recorded.

In the event of a Grade 2 IRR that does not improve or worsens after implementation of the treatment modifications indicated in [Table 4](#) (including reducing the infusion rate by 50%), the Investigator may consider treatment with corticosteroids and the infusion should be stopped for that day. At the next infusion, the Investigator may consider the addition of H2 blocker antihistamines (e.g., famotidine or ranitidine), in addition to premedication, for select participants. However, prophylactic steroids are not permitted. At the next dose, if the participant has a second IRR Grade  $\geq$  2 on the slower infusion rate, with the addition of further medication to premedication, the infusion should be stopped, and the participant should be removed from the study intervention.

### Hypersensitivity Reaction

If a hypersensitivity reaction occurs, the participant must be treated according to the best available medical practice. A complete guideline for the emergency treatment of anaphylactic reactions according to the Working Group of the Resuscitation Council United Kingdom and can be found

at <https://www.resus.org.uk/pages/reaction.pdf>. Participants should be instructed to report any delayed reactions to the Investigator immediately.

Symptoms may include, but are not limited to:

- Impaired airway
- Decreased oxygen saturation (< 92%)
- Confusion
- Lethargy
- Hypotension
- Pale/clammy skin
- Cyanosis.

Management of hypersensitivity includes:

- Epinephrine injection and intravenous dexamethasone
- Participant should be placed on cardiac, blood pressure, heart rate, and oxygen saturation monitoring immediately
- Alert intensive care unit for possible transfer if required.

#### **Prophylaxis of Flu-Like Symptoms:**

For prophylaxis of flu-like symptoms, a nonsteroidal anti-inflammatory drug (NSAID), e.g., ibuprofen 400 mg or comparable NSAID dose, may be administered 2 hours before and 8 hours after the start of each intravenous infusion.

#### **6.9.2 Immune-Related Adverse Events**

In general, the spectrum of irAEs is similar for M7824 compared with other checkpoint inhibitors. Immune-related AEs are considered AESIs. Effective risk management of these toxicities (irAEs) primarily caused due to inhibition of PD-L1 and PD-1 pathways is based on key recommendations ([Champiat 2016](#)). Participant education for on-time reporting of symptoms of potential irAEs and prompt clinical assessment is critical for effective management and quicker resolution of immune-mediated toxicities, thus preventing progression into severe forms of toxicity that otherwise may become life-threatening and difficult to manage or warrant permanent discontinuation from the study.

Immune-related AEs are specific to immunotherapies and vary by organ system.

The following immune-related AEs are important identified risks for M7824:

- Immune-related hepatitis
- Immune-related pneumonitis
- Immune-related colitis

- Immune-related nephritis and renal dysfunction
- Immune-related endocrinopathies (thyroid disorders, adrenal insufficiency, Type 1 diabetes mellitus, pituitary disorders)
- Immune-related rash
- Other immune-related events (myositis, myocarditis, encephalitis)

The following irAEs are important potential risks for M7824:

- Guillain-Barré syndrome
- Uveitis
- Pancreatitis
- Myasthenia gravis/myasthenic syndrome

The Medical Monitor may be involved as needed for follow-up. Details of the diagnostic work-up will be requested by the study team.

For treatment management of irAEs per NCI-CTCAE v5.0 criteria, refer to the ASCO Clinical Practice Guidelines and National Comprehensive Cancer Network (NCCN) irAE management guidelines.

The recommendations for irAE management are guided by the joint ASCO Clinical Practice Guidelines (Brahmer 2018) and NCCN guidelines, listed in [Appendix 6](#).

Treatment of irAEs is mainly dependent upon severity as defined by NCI-CTCAE v5.0. In general, management by NCI-CTCAE v5.0 grading, as per ASCO, is listed below:

- Grade 1: study intervention should be continued with close monitoring, with the exception of some neurologic, hematologic, and cardiac toxicities.
- Grade 2: study intervention may be suspended for most Grade 2 toxicities, with consideration of resuming when symptoms revert to Grade 1 or less. Corticosteroids may be administered (initial dose of 0.5 to 1 mg/kg/day of prednisone or equivalent).
- Grade 3: study intervention is generally suspended and high-dose corticosteroids (prednisone 1 to 2 mg/kg/day or methylprednisolone 1 to 2 mg/kg/day) treatment should be initiated. Corticosteroids should be tapered over the course of at least 4 to 6 weeks. Some refractory cases may require infliximab or other immunosuppressive therapy.
- Grade 4: in general, permanent discontinuation of study intervention is recommended, with the exception of endocrinopathies that have been controlled by hormone replacement.

Permanent treatment discontinuation is required in case of immune-related Grade 4 rash/inflammatory dermatitis, nephritis, autoimmune hemolytic anemia, hemolytic uremic syndrome, aplastic anemia, immune thrombocytopenia and acquired thrombotic thrombocytopenic purpura (TTP).

For Grade 4 immune-related lymphopenia, permanent discontinuation of study intervention will be required, if lymphopenia is considered immune-related in nature, no clear alternative explanation exists for the event, and Grade 4 lymphopenia does not resolve within 14 days. Permanent discontinuation of study intervention is not required when the AE is manifest by a single laboratory value out of normal range without any clinical correlates. In this case, study intervention should be held until the etiology is determined. If the event is not considered immune-related and resolves to Grade  $\leq 1$  restarting of study intervention may be considered.

For additional organ/system specific management guidelines, see the guideline tables in [Appendix 6](#).

Recommended guidance and management for specific irAEs are provided in the current NCCN guideline available at <http://www.nccn.org>.

